9.2 Type and Duration of Follow-up of Subjects after Adverse Events

All AEs as described above will be followed until resolved or considered stable.

9.3 Halting Rules

9.3.1 Discontinue of Study participation for individual subject

Subjects who experience significant problems with blood draws may be withdrawn from any future sampling.

9.4 FDA MedWatch Adverse Event Reporting Program

Reporting of adverse events related to drug administration is not part of the protocol. The reporting is in support of the FDA post-marketing safety surveillance program and is encouraged.

The FDA MedWatch adverse event reporting program allows health care professionals to voluntarily report a serious adverse event, product quality problem or product use error that is suspected to be associated with the use of an FDA-regulated drug, biologic, medical device or dietary supplement. This system is for the reporting of adverse events noted spontaneously in the course of clinical care, and not for events that occur during clinical trials under an Investigational New Drug (IND) application.

The MedWatch Website, <http://www.fda.gov/Safety/MedWatch/HowToReport/ucm085568.htm> can be used to voluntarily report a serious adverse event, product quality problem or product use error that is suspected to be associated with the use of an FDA-regulated drug, biologic, medical device, dietary supplement or cosmetic. FDA uses these data to maintain safety surveillance of all FDA-regulated products. A health care professional report may be the critical action that prompts a modification in use or design of the product, improves the safety profile of the drug or device and leads to increased patient safety.

10 CLINICAL MONITORING

10.1 Monitoring Plan

Monitoring of study will be conducted to ensure that human subject protection, study procedures, laboratory procedures, study intervention administration, and data collection processes are of high quality and meet regulatory guidelines, and that the study is conducted in accordance with the protocol and study manuals. A Clinical Monitoring Plan will not be developed.

If conducted, monitoring visits will include but are not limited to review of regulatory files, case report forms, informed consent forms, medical and laboratory reports, and protocol compliance. COA research nurses will meet with investigators to discuss any problems and actions to be taken and document visit findings and discussions.

Every effort will be made to maintain the anonymity and confidentiality of subjects during this study.

11 STATISTICAL CONSIDERATIONS

11.1 Study Hypotheses

Our primary hypothesis is that valacyclovir at 20 mg/kg every 8 hours when administered to very young infants will provide adequate exposure to the active metabolite, acyclovir, and be comparable to intravenous acyclovir 20 mg/kg every 8 hours.

11.2 Sample Size Considerations

The primary endpoint for this study is to determine if 20 mg/kg of valacyclovir every 8 hours is comparable to 20 mg/kg of intravenous acyclovir every 8 hours. Thus, based on investigator experience, feasibility, and low kinetic variability secondary to renal excretion, a sample size of 6 and up to 10 subjects will be enrolled. Data will be collected on standardized case report forms. Standard non-compartmental techniques will be used initially to estimate pharmacokinetic parameters derived from the acyclovir concentration time data. The resource utilized for pharmacokinetic analysis is WinNonlin version 5.3, Pharsight Corporation, Mountain View, CA.

11.3 Planned Interim Analyses (if applicable)

There are no planned interim analyses for this trial.

11.4 Final Analysis Plan

Descriptive statistics will be represented by means, standard deviations, and confidence intervals for continuous variables and counts and proportions for categorical variables.

Primary analysis: Acyclovir and valacyclovir pharmacokinetic parameters will initially be determined using non-compartmental analysis (WinNonlin v5.3) for each individual subject. The parameters (AUC_8 , CL, Vd, etc.) will be summarized and further used for exploratory pharmacodynamic analysis.

To compare how the valacyclovir PK as measured by AUC_8 in infants diagnosed with neonatal HSV disease differ from acyclovir PK as measured by AUC_8 in the same subset of patients, we will construct 95% confidence intervals around the mean AUC_8 and compare these means across the subset of patients. Additional pharmacokinetic parameters that compose analyses for secondary endpoints include C_{max} , $T_{1/2}$, CL, and Vd.

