3.2 Study Outcome Measures

3.2.1 Primary Outcome Measures

Primary Endpoint:

- Plasma pharmacokinetic parameters for valacyclovir AUC_8
- Cumulative incidence of Grade 3 or higher unsolicited adverse events, serious adverse events, or any adverse event that is not recovered / not resolved

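### AUC_8 and the other PK parameters are summarised only by means, SDs and 95% CIs; adding log-scale (geometric) summaries is a minor, near-free improvement

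*Combined protocol and SAP*

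**What the plan says.** Section 11.4 sets the general rule for continuous variables: "Descriptive statistics will be represented by means, standard deviations, and confidence intervals for continuous variables". For the oral-to-IV comparison it adds: "we will construct 95% confidence intervals around the mean AUC_8 and compare these means across the subset of patients". The individual non-compartmental parameters (AUC_8, CL, Vd and others) "will be summarized and further used for exploratory pharmacodynamic analysis". The same section lists Cmax, T1/2, CL and Vd as further parameters for the secondary endpoints.

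Nothing in 11.4 mentions a log transformation, geometric mean, geometric CV, median or range. The words arithmetic and raw scale do not appear either, and the type of interval (t or normal) is not given. Arithmetic summaries are the natural reading of a mean paired with an SD.

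These summaries apply to the primary PK endpoint in Section 3.2.1, "Plasma pharmacokinetic parameters for valacyclovir AUC_8". Section 11.2 states that "a sample size of 6 and up to 10 subjects will be enrolled" and gives the grounds as "based on investigator experience, feasibility, and low kinetic variability secondary to renal excretion". No CV or SD for AUC_8 appears anywhere.

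**The concern.** AUC equals bioavailability times dose divided by clearance. A quantity built from products and quotients of positive terms tends to be right-skewed, and the same holds for Cmax, CL and Vd. With 6 to 10 infants, one slow-clearing infant moves both the mean and the SD, and averaging over so few subjects does not remove the skew.

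Two consequences are possible. First, the interval for each treatment's mean may fall short of 95% and miss more often on the low side. For AUC_8 and Cmax, a low miss understates exposure. That direction deserves attention here, because Section 2.1 reports higher AUC and Cmax in infants of 1-2 months, attributed to reduced clearance. Second, Section 11.1 asks whether oral and IV exposure are comparable. If oral AUC varies more than IV AUC, a comparison of arithmetic means partly reflects that difference in spread.

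The point concerns the scale of each treatment's summary. How the plan uses the pairing of the two treatments within infants is a separate matter.

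**Working it through.** **Inputs.** From the documents: n = 6 to 10 (11.2) and a 95% confidence level around the mean AUC_8 (11.4). Assumed: log-normal AUC_8, with a between-infant CV of 20% to 50% as the main range and 100% as an extreme.

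**The plan's own figure.** The sample size cannot be reproduced, because no SD, margin, power or precision target is given. The only stated error figure is the nominal 95%.

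**Coverage of the planned interval.** The log-scale SD is s = sqrt(ln(1 + CV²)). For each setting, 400,000 samples were drawn with true arithmetic mean 1. The interval was mean ± t(0.975, n−1) × SD / sqrt(n), and misses on each side were counted separately.

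| CV | n | Coverage of arithmetic mean | Interval wholly below | Interval wholly above | Share of misses below |
|---|---|---|---|---|---|
| 20% | 6 | 94.5% | 4.1% | 1.4% | 74% |
| 20% | 10 | 94.5% | 4.0% | 1.5% | 74% |
| 30% | 6 | 93.9% | 5.1% | 1.1% | 83% |
| 30% | 10 | 94.0% | 4.9% | 1.1% | 81% |
| 40% | 6 | 92.9% | 6.3% | 0.8% | 88% |
| 40% | 10 | 93.3% | 5.9% | 0.8% | 87% |
| 50% | 6 | 91.9% | 7.5% | 0.6% | 92% |
| 50% | 10 | 92.4% | 6.9% | 0.7% | 91% |
| 100% | 6 | 86.0% | 13.8% | 0.2% | 99% |
| 100% | 10 | 87.2% | 12.6% | 0.2% | 98% |

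The loss is therefore about 0.5 to 1 point at CV 20-30% and about 3 points at CV 50%. Moving from 6 to 10 infants changes little.

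**Log-scale interval.** A t-interval on log(AUC_8), back-transformed, covers the geometric mean in 94.9-95.1% of samples at every CV and n tried, with symmetric misses. This is exact under log-normality.

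**The target changes.** Geometric mean / arithmetic mean = 1 / sqrt(1 + CV²):
- CV 20%: 1 / sqrt(1.04) = 0.98
- CV 30%: 1 / sqrt(1.09) = 0.96
- CV 50%: 1 / sqrt(1.25) = 0.89

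**Effect on an oral-to-IV ratio.** Ratio of arithmetic means / ratio of geometric means = sqrt((1 + CV_oral²) / (1 + CV_IV²)), with assumed CVs:
- 40% oral, 30% IV: sqrt(1.16 / 1.09) = 1.03
- 50% oral, 30% IV: sqrt(1.25 / 1.09) = 1.07

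**The case against.** The strongest objection is that the log-scale interval reaches 95% only by changing what is estimated. Scored against the same arithmetic mean, it does no better. At n = 6 and CV 30% it lies wholly below that mean in 4.8% of samples, against 5.1% for the planned interval. At n = 10 and CV 50% it does so in 9.9%, against 7.0%. Conversely, the planned interval covers the geometric mean in 94.7-95.3% of samples at CV 20-60%. This stands. A reader might infer that the plan will understate exposure and that log-scale analysis would cure it; the calculation does not support the second half of that inference.

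The size of the loss also rests on CVs that the documents do not supply, and Section 11.2 describes variability as low. This stands too. A reader might conclude that the planned interval is seriously wrong, or that it misses almost only on the low side. That needs a CV of about 50% or more, and no passage states one. On the other hand, low variability is asserted rather than shown. The sample pools infants of 2-12 weeks, and oral dosing uses a compounded suspension given with or without food, by mouth or by tube (6.2.1, 6.2.2).

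Three further limits apply:
- Understated exposure describes a low miss for AUC_8 and Cmax only. For CL a low miss points the other way, and Vd and T1/2 are not exposure measures.
- The under-coverage concerns a single treatment's mean. A paired raw-scale difference, simulated at CVs of 30-80%, covers 95.2-96.7% with symmetric misses when the two true means are equal.
- The 3% and 7% are differences between two quantities, not biases. The plan sets no comparability margin that such a shift could cross.

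Finally, 11.4 does not forbid log-scale output. The gap is under-specification in a small descriptive study.

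**Conclusion.** The point holds as a minor one. Section 11.4 specifies only means, SDs and 95% intervals for positive, multiplicative PK parameters in 6 to 10 infants. Under log-normality, the raw-scale t-interval for the arithmetic mean loses about 0.5 to 1 point of coverage at CV 20-30% and about 3 points at CV 50%. Low misses make up 74% of all misses at CV 20%, 81-83% at CV 30% and over 90% from about CV 50%. All of this depends on assumed CVs and on the log-normal model.

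What log-scale summaries add is an interval with nominal, symmetric coverage of a clearly stated target, slightly narrower intervals (about 6% at n = 10 and CV 50%), and an oral-to-IV ratio that unequal variability does not shift. This is a worthwhile convention to write down. It does not correct an error in any stated figure.

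**What to change.** In Section 11.4, for each treatment:
- Analyse AUC_8, Cmax, CL, Vd and T1/2 on the log scale, and report the geometric mean, geometric CV and back-transformed 95% t-interval.
- Add the median, the range and a listing of individual values, which is practical with 6 to 10 infants.
- Keep the arithmetic mean and SD.
- Express the oral-to-IV comparison of AUC_8 as a ratio of geometric means.
- State that the log-scale interval is for the geometric mean and must not be read as an interval for the arithmetic mean or as a remedy for understating it.

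The cost is a few lines of SAP wording. No extra blood, visits or subjects are needed, and these summaries are routine output for PK software.

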3 OBJECTIVES

3.1 Study Objectives

Primary:

- To define the pharmacokinetics of valacyclovir in neonates (\geq 34 weeks gestational age at birth and \geq 2000 g)
- To assess safety of valacyclovir administration

Secondary:

- To assess the pharmacokinetics of high-dose parenteral acyclovir in neonates \geq 34 weeks gestation with virologically confirmed neonatal HSV disease who are receiving acyclovir as standard of care
- To compare the pharmacokinetics of high-dose parenteral acyclovir to the pharmacokinetics of the proposed study dose of valacyclovir (20 mg/kg every 8 hours)

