3.2.2 Secondary Outcome Measures

Secondary Endpoints:

- Plasma pharmacokinetic parameters for parenteral acyclovir AUC_8
- Comparison of AUC_8 of 20 mg/kg IV acyclovir to the AUC_8 of 20 mg/kg PO valacyclovir

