Upon completion of the intravenous acyclovir per standard of care, the infant will be switched to valacyclovir 20 mg/kg every 8 hours for 2 and up to 7 days depending upon availability of the CHRU. The first dose of valacyclovir is to be given 8 hours after completion of the last dose of IV acyclovir. On day 2 (up to 7), the infant will return to UAB's CHRU for a PK profile to be obtained. The plasma specimens for the pharmacokinetic profile will be drawn at hour 0 (just prior to the scheduled valacyclovir dose and 8 hours after the last dose), at 1-2 hours after dose for a peak level, and 3-5 hours after dose. Once the infant completes the pharmacokinetic sampling, the infant will have completed the study and will be switched to oral acyclovir per standard of care guidelines to complete 6 months of oral suppressive therapy for neonatal HSV disease. The parent(s) or guardian will be instructed to have the infant follow with an infectious disease specialist for appropriate follow up of neonatal HSV disease while on suppressive therapy.

All participants will receive the standard of care treatment with 14 to 21 days of IV acyclovir (depending on disease classification) followed by 6 months of oral antiviral suppression. The only change is that the first few days of oral suppression will be with valacyclovir instead of acyclovir. Subjects with inadequate pharmacokinetic data for analysis (e.g., due to dropping out of the study before PK assessments are performed or blood sampling obtained but is

inadequate for analysis) may be replaced and will not count toward the total of 6 and up to 10 subjects.

Treatment Day 1 is the calendar day when the first dose of parenteral acyclovir was administered to the study subject for clinical purposes and will be the date against which follow-up visits will be defined. **Treatment Dose 1** corresponds to the first dose of parenteral acyclovir given to the study subject for clinical purposes. The study enrollment day is unlikely to be the same day as Treatment day 1 as individuals will need confirmation of neonatal HSV infection in order to be enrolled. Participants can enroll on or before treatment day 14. **Study Assessment Day 1** is the calendar day when the participant is enrolled in the study.

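### Section 11.4 compares oral and IV AUC8 in the same infants through intervals around mean AUC8, and specifies no within-infant oral/IV ratio or interval for one

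*Combined protocol and SAP*

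**What the plan says.** Section 11.4 (Final Analysis Plan) derives AUC8 by non-compartmental analysis for each infant. It then asks how valacyclovir exposure may "differ from acyclovir PK as measured by AUC_8 in the same subset of patients", and gives the method: "we will construct 95% confidence intervals around the mean AUC_8 and compare these means across the subset of patients". Continuous variables are summarised by means, standard deviations and confidence intervals. No log scale, ratio, difference or paired method is named.

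The question itself appears in several places:

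- Section 11.1 hypothesises that oral exposure will be adequate "and be comparable to intravenous acyclovir 20 mg/kg every 8 hours".
- Section 11.2 states: "The primary endpoint for this study is to determine if 20 mg/kg of valacyclovir every 8 hours is comparable" to the IV regimen.
- Section 3.1 lists the comparison as a secondary objective: "To compare the pharmacokinetics of high-dose parenteral acyclovir to the pharmacokinetics of the proposed study dose of valacyclovir".
- Section 3.2.2 lists it as a secondary endpoint: "Comparison of AUC_8 of 20 mg/kg IV acyclovir to the AUC_8 of 20 mg/kg PO valacyclovir".

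The sample is 6 to 10 infants, justified partly by "low kinetic variability secondary to renal excretion". Section 4 plans one IV profile per infant between doses 22 and 42 and one oral profile on day 2 to 7 of valacyclovir. It allows enrolment up to Treatment Day 14. Subjects with inadequate PK data "may be replaced and will not count toward the total of 6 and up to 10 subjects".

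**The concern.** The design gives two AUC8 values from the same infant, and the question is how one relates to the other. Two intervals, one per drug, do not answer it. They describe how well each mean is known, not how well the ratio of the two is known. The ratio's uncertainty depends on the within-infant correlation, which separate summaries leave out. A reader of the report could not recover it without the individual data.

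Two related points are also open. Section 11.2 treats the comparison as primary, while Sections 3.1 and 3.2.2 treat it as secondary. And it is only partly settled which infants enter it: an infant enrolled late may have an oral profile and no IV profile, so two separate means could come from different sets of infants.

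**Working it through.** **What can be reproduced.** The plan gives no SD, CV, correlation, margin or power, so it has no calculated figure to reproduce. The sample size of 6 to 10 is stated without a formula. Everything numerical below is illustration.

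**Assumptions (not in the documents).** AUC8 lognormal; equal CV on both routes, 20% to 50%; log-scale within-infant correlation ρ from 0 to 0.8. Log-scale SD: s = √ln(1 + CV²), which is 0.198 at CV 20%, 0.385 at 40% and 0.472 at 50%.

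**Step 1: what separate intervals leave out.** 95% intervals as multiply/divide factors:

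- one drug's geometric mean: exp(t(n−1) · s / √n), with no ρ in it;
- paired oral/IV ratio: exp(t(n−1) · s · √(2(1−ρ)/n)).

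With n = 6 and CV 40%, t(5) = 2.571. One mean: exp(2.571 × 0.385 / √6) = 1.50. At CV 40%:

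| n | Each mean | Ratio, ρ = 0 | Ratio, ρ = 0.5 | Ratio, ρ = 0.8 |
|---|---|---|---|---|
| 6 | 1.50 | 1.77 | 1.50 | 1.29 |
| 10 | 1.32 | 1.48 | 1.32 | 1.19 |

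The same pair of separate intervals is compatible with every ratio interval in its row.

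**Step 2: what pairing gains over treating the two sets as independent.** Relative width on the log scale = √(1−ρ) × t(n−1) / t(2n−2). The t quotient is 2.571/2.228 = 1.154 for 6 pairs and 2.262/2.101 = 1.077 for 10.

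| Pairs | ρ = 0 | 0.3 | 0.5 | 0.7 | 0.8 |
|---|---|---|---|---|---|
| 6 | 1.15 | 0.97 | 0.82 | 0.63 | 0.52 |
| 10 | 1.08 | 0.90 | 0.76 | 0.59 | 0.48 |

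Pairing narrows the interval when ρ exceeds 1 − (t(2n−2)/t(n−1))²: about 0.41 with 4 pairs, 0.25 with 6 and 0.14 with 10.

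**Step 3: in units of the ratio.** The unpaired factor is exp(t(2n−2) · s · √(2/n)). For CV 20% to 50%:

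| n | Paired, ρ = 0.7 | Paired, ρ = 0.5 | Unpaired |
|---|---|---|---|
| 6 | 1.17 to 1.47 | 1.23 to 1.64 | 1.29 to 1.84 |
| 10 | 1.12 to 1.30 | 1.15 to 1.40 | 1.20 to 1.56 |

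With only 4 pairs at ρ = 0.7, the paired factor is 1.28 to 1.79.

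**Step 4: judging by eye from two intervals.** The plan states no overlap rule, so this only shows what an informal reading could do. Take a true oral/IV ratio of 0.75, CV 30% and ρ = 0.5. In simulation, two separate 95% intervals overlap in about 95% of trials with 6 infants and 84% with 10. The paired interval excludes 1 in about 49% and 79%.

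**Step 5: which infants form a pair.** At three doses a day, 42 doses take 42/3 = 14 days, so the IV sampling window closes at about the end of Day 14. Enrolment is open until that same day. Section 4 includes infants in whichever periods they are eligible for. Replacement is optional, and its examples do not mention late enrolment. An oral-only infant is therefore possible.

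**The case against.** The strongest reply is that the plan is silent rather than wrong. AUC8 is derived per infant and the comparison is confined to the same infants, so a paired analysis fits the wording. If only infants with both profiles are used, the difference of the two means equals the mean within-infant difference, and the point estimate of that contrast is not lost. Individual values will exist, so a ratio can be computed later. This is a small descriptive Phase IB study, and the separate means do address the adequate-exposure half of the hypothesis. All of this is fair. It does not supply the missing interval, and it leaves the estimator to be chosen after the assays are read.

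A second reply is that the gain from pairing is uncertain. This also stands in part. The correlation may be modest: the profiles can be weeks apart, Section 2.1 describes lower clearance in the youngest infants, and each AUC8 rests on three samples. If the oral log-SD were twice the IV log-SD, the break-even correlation with 6 pairs would rise from 0.25 to about 0.31. The paired-against-unpaired figures also compare two analyses that the plan does not name. The case therefore rests mainly on the absence of any interval for the contrast, which holds at every correlation. The precision gain is secondary.

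**Conclusion.** The concern holds and should be fixed. No section supplies an oral/IV contrast or an interval for one, so the plan as written leaves its central comparison without stated uncertainty. That conclusion comes from the text and needs no assumption. The size does: with log-scale correlation 0.5 to 0.8, a paired interval would be 0.82 to 0.52 times the unpaired width with 6 pairs and 0.76 to 0.48 times with 10. Below a correlation of about 0.25 (6 pairs) or 0.14 (10 pairs), pairing would not narrow it. The data remain analysable either way, so this is a defect of specification and reporting rather than a fatal one. The primary/secondary conflict between Section 11.2 and Sections 3.1 and 3.2.2 needs resolving at the same time.

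**What to change.** Replace the comparison sentence in Section 11.4 with text such as:

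> For infants with both an IV and an oral profile, compute ln(AUC8 oral) − ln(AUC8 IV). Report the geometric mean oral/IV ratio with a paired t-based 95% confidence interval, the number of pairs and each individual ratio. Infants with only one profile are summarised separately. Comparability will not be inferred from overlap of separate intervals.

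State once whether the comparison is primary or secondary, and align Sections 3.1, 3.2.2 and 11.2. Note as a limitation that IV always precedes oral, so any maturation between the profiles stays in the ratio.

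**Cost.** A few lines of text, with no new samples or infants. Infants without an IV profile leave the comparison. If the correlation were zero, the paired interval would be 15% wider than the unpaired one with 6 pairs and 8% wider with 10. The interval may still be wide.

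A reference range for 'comparable' is optional and for the sponsor to choose before assays are read; if one is used, name a single confidence level. It would often not be met. With an illustrative range of 0.80 to 1.25, a true ratio of 1 and correlation 0.7, the 95% interval lies inside in 65% of trials at CV 20% and 7% at CV 40% with 6 infants, and in 97% and 22% with 10. Reporting the ratio and its interval without a verdict avoids that cost.
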